4.1.1. CAM2038 q1w (Once Weekly)

SC CAM2038 q1w has so far been investigated after single and repeated doses in 7 clinical trials in opioid-dependent subjects and healthy volunteers. An initial Phase 1/2 study assessed pharmacokinetics (PK), pharmacodynamics, and safety in opioid-dependent subjects (Study HS-07-307). The results showed that CAM2038 q1w was well tolerated, both locally and systemically. Importantly, no treatment-emergent serious adverse events (SAEs) were observed and drug-related local tolerability findings were limited to 4 of 42 subjects (9.5%). Three subjects experienced mild injection site pain and 1 patient exhibited transient injection site inflammation (mild) and injection site pruritus (moderate).

Two additional clinical Phase 1 studies were subsequently performed in healthy volunteers (under naltrexone blockade) to assess the PK and bioavailability of single and repeat doses of CAM2038 q1w versus repeated doses of sublingual (SL) BPN (i.e., at steady state) and single dose of intravenous (IV) BPN (Studies HS-11-426 and HS-13-487). These two studies demonstrated that after administration of the studied doses of CAM2038 q1w, the plasma concentrations corresponded to those obtained after administration of SL BPN at approved doses (i.e., 8 mg, 16 mg, or 24 mg doses). The BPN levels after administration of CAM2038 q1w were furthermore similar in healthy volunteers and subjects with opioid dependence. The systemic tolerability of CAM2038 q1w was good in both studies and similar to the reference products, IV and SL BPN. Local tolerability was very good with no adverse events (AEs)

reported in Study HS-11-426 (N_{safety}=60) related to injection site tolerability. Similarly, local tolerability of CAM2038 q1w was also very good in Study HS-13-487, featuring 4 repeat injections of CAM2038 q1w into the buttock site (1 subject reported 1 AE of injection site pain).

Based on these studies, the following main conclusions were drawn regarding the clinical properties of CAM2038 q1w:

- Extended BPN release over one week
- Dose proportionality and flexible/multiple dosing options
- Six- to 8-fold higher bioavailability versus SL BPN
- BPN plasma concentrations over 7 days within ranges of those produced by corresponding SL BPN doses at steady state (i.e., approved 8 mg, 16 mg or 24 mg doses)
- Less peak/trough fluctuation compared to SL BPN
- Repeated-dose administration suggest time-independent PK

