4.2. Study Rationale

Chronic low back pain (CLBP) is a significant cause of pain and disability costs worldwide ([Volinn et al, 2009](#); [Vos et al, 2012](#)). While most subjects with CLBP show significant improvements within 3 months, a proportion of subjects experience persistent pain (≥ 3 months) and may have limited quality of life and physical function ([Shekelle et al, 1995](#); [Thomas et al, 1999](#)). Management of CLBP may be achieved through several modalities, including opioid pharmacotherapy. Despite their proven efficacy, the use of opioids is often limited due to concerns regarding safety and tolerability and concerns pertaining to drug abuse and diversion that may arise with long-term therapy for treatment of persistent pain. However, for many subjects with CLBP, opioid therapy may be the only effective treatment. BPN is an effective analgesic with a potency 25 to 50 times that of morphine ([Jasinski et al, 1978](#); [Cowan et al, 1977](#)). Dose-dependent analgesia has been observed with intramuscular (IM) doses up to 10 mg. Respiratory depression is minimized due to the well-characterized ceiling effect at higher doses ([Hans and Robert, 2009](#)). Clinically, there is also a less marked effect of BPN on gastrointestinal transit times, with a lower incidence of constipation relative to full mu-opioid receptor agonists ([Mercadente, 2009](#)). In addition, the slow dissociation of BPN from receptors results in a long duration of effect and minimizes withdrawal symptoms upon discontinuation ([Sittl et al, 2005](#)). Transdermal BPN has proven effective in subjects with chronic cancer and non-cancer pain, with a reduction in the need for additional oral analgesics and improved quality of life ([Mercadente, 2009](#); [Dahan et al, 2005](#); and [Griessinger et al, 2005](#)).

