4.3. Dose Rationale

The 4-mg weekly starting dose of CAM2038 q1w correspond to a daily morphine equivalent dose (MED) of 28.5 mg, using a more conservative conversion factor of 50 from BPN to morphine; thus, representing safe and suitable starting doses for subjects receiving ≥ 30 mg of morphine daily. In this study, subjects will be titrated to effect. An indicative a priori transition from daily morphine dose to weekly CAM2038 doses and monthly CAM2038 dose is given in Table 1 and Table 2 below, respectively:

Table 1: Conversion from Daily Morphine to Once Weekly CAM2038 Doses

Daily Morphine Dose (mg)	Daily Titration Morphine Dose, 75 % (mg)	Starting Once Weekly Dose
40 to <80	30 to 60	4 mg CAM2038
80 to 120	60 to 90	8 mg CAM2038
>120 to 160	90 to 120	16 mg CAM2038
>160 to 320	120 to 240	24 mg CAM2038
>320	>240	32 mg CAM2038

Table 2: Conversion from Once Weekly CAM2038 to Once Monthly CAM2038 Dose

Once Weekly Dose	Corresponding Once Monthly CAM2038 Dose
4 mg CAM2038	No corresponding monthly dose. Subjects will be kept on CAM2038 once weekly.
8 mg CAM2038	No corresponding monthly dose. Subjects will be kept on CAM2038 once weekly.
12 mg CAM2038	No corresponding monthly dose. Subjects will be kept on CAM2038 once weekly.
16 mg CAM2038	64 mg CAM2038
24 mg CAM2038	96 mg CAM2038
32 mg CAM2038	128 mg CAM2038

The MED will be calculated using the conversion factor for each opioid as described in [Table 3](#) (McPherson, 2009). Subjects taking methadone are allowed to screen; however, the down titration process should be discussed with the Medical Monitor.

Table 3: Opioid Conversion to Morphine Equivalent Dose

Equianalgesic Opioid Dosing			
Drug	Equianalgesic Doses (mg)		
	Parenteral	Oral	Sublingual
Sublingual Buprenorphine	NA	NA	1.5
Belbuca™ buccal film	NA	0.3	NA
Morphine	10	30	NA
Codeine	100	200	NA
Hydrocodone	NA	30	NA
Hydromorphone	1.5	7.5	NA
Meperidine	100	300	NA
Oxycodone	10*	20	NA
Oxymorphone	1	10	NA
Tramadol	100*	120	NA
		Morphine (PO) Equivalents	
*Fentanyl Patch 25mcg/hr (One patch q3 days)	NA	60 mg / d	NA
Butrans patch 10mcg/hr (One patch q week)	NA	80 mg / d	NA
*Methadone 20 mg PO qd	NA	40 mg / d	NA

* Contact Medical Monitor to discuss

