7.1. Inclusion Criteria

Subjects must meet all of the following inclusion criteria in order to be eligible for participation in the study:

1. Written informed consent provided prior to the conduct of any study-related procedures.
2. Male or non-pregnant, non-lactating female subject, greater than or equal to 18 years old.
3. Body mass index (BMI) between 18 and 38 kg/m², inclusive.
4. Treated with daily opioids for moderate to severe CLBP for a minimum of 3 months prior to Screening.
5. On a stable dose of ≥ 40 mg/day of oral morphine or MED during the 14 days prior to Screening.
6. Systolic blood pressure ≥ 100 mmHg and diastolic blood pressure ≥ 60 mmHg.
7. Female subject of childbearing potential who is willing to use a reliable method of contraception during the entire study (Screening Visit to final Follow-up; see Section 9.1.5). To be considered not of childbearing potential, female subjects must be surgically sterile (hysterectomy or bilateral oophorectomy, or bilateral tubal ligation with surgery at least 6 weeks before Screening).
8. Male subject who is willing to use reliable contraception.
9. Willing and able to comply with all study procedures and requirements.

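### Protocol Section 4.3 converts buprenorphine to morphine at 50 in the dose rationale but at an implied 333 in Table 3's patch row, which decides entry and dose band for patch users

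*Protocol*

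**What the plan says.** Protocol Section 4.3 does two things with buprenorphine potency.

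- **Dose rationale.** It states that "The 4-mg weekly starting dose of CAM2038 q1w correspond to a daily morphine equivalent dose (MED) of 28.5 mg", obtained by "using a more conservative conversion factor of 50 from BPN to morphine", and describes this as "representing safe and suitable starting doses for subjects receiving ≥ 30 mg of morphine daily". Section 4.2 gives the wider potency range: "BPN is an effective analgesic with a potency 25 to 50 times that of morphine". It does not say by which route.
- **Screening MED.** The same section says "The MED will be calculated using the conversion factor for each opioid as described in" Table 3. That table has three buprenorphine rows: sublingual 1.5 mg and buccal film 0.3 mg, each set against 30 mg oral morphine, and the row "Butrans patch 10mcg/hr (One patch q week", set equal to 80 mg/day oral morphine.

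Screening MED is then used as follows:

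- Entry (Section 7.1): "On a stable dose of ≥ 40 mg/day of oral morphine or MED during the 14 days prior to Screening". Section 9.5 uses the same 40 mg/day to define opioid-experienced subjects.
- Starting dose and optional second dose in week 1 (Section 8.1.3): set by whether screening MED is 40-79 or at least 80 mg/day.
- Rescue ceiling (Section 8.1.4): three or six tablets a day by the same split.

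Subjects already on buprenorphine may enter. They skip immediate-release morphine but follow the same Day 1 procedures (Section 7.3). On bioavailability, Section 4.1.1 reports "Six- to 8-fold higher bioavailability versus SL BPN" for weekly CAM2038.

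**The concern.** The dose rationale and Table 3 serve the same purpose: to match prior opioid exposure to a CAM2038 dose on a common morphine scale. If buprenorphine is placed on that scale one way when it is the study drug and another way when it is the prior medication, a prior-buprenorphine subject's MED is not comparable with the MED that the protocol attaches to the first injection.

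For the patch row the gap is large enough to move a subject across both cut-offs, 40 and 80 mg/day. What is at stake is whether such a subject has the opioid exposure that Section 9.5 requires, and which starting dose, booster and rescue ceiling apply. Table 3's footnote refers the fentanyl-patch and methadone rows to the Medical Monitor. No buprenorphine row is so marked, so on the face of the table the 80 mg/day figure is used as printed.

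**Working it through.** **1. Reproduce the protocol's own figure.** 4 mg weekly is 4/7 = 0.571 mg/day. At 50 this is 0.571 × 50 = 28.6 mg/day, against 28.5 stated. The figure reproduces, apart from truncation. By the same rule 8 mg weekly is 8/7 × 50 = 57.1 mg/day.

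**2. Factor implied by the patch row.** Assumption: the labelled 10 mcg/hr is delivered for 24 hours.

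- Delivered dose: 10 × 24 / 1000 = 0.24 mg/day.
- Implied factor: 80 / 0.24 = 333.
- Ratio to the dose rationale: 333 / 50 = 6.7.

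**3. The same patch by every other conversion in the protocol.**

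| Source | Factor to oral morphine | MED of 0.24 mg/day |
|---|---|---|
| Section 4.3 dose rationale | 50 | 12 mg/day |
| Section 4.2 range of 25-50, read as parenteral, × Table 3's 30:10 oral-to-parenteral morphine ratio | 75-150 | 18-36 mg/day |
| Table 3 buccal row, nominal (30 / 0.3) | 100 | 24 mg/day |
| Table 3 sublingual row (30 / 1.5 = 20) × 6 to 8 from Section 4.1.1 | 120-160 | 28.8-38.4 mg/day |
| Table 3 patch row | 333 | 80 mg/day |

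Only the patch row reaches 40 mg/day, and it also reaches 80.

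**4. Distance from the cut-offs.** At 50, the patch rate needed is 40 / 50 / 24 × 1000 = 33 mcg/hr for the entry criterion and 67 mcg/hr for the upper band. At the most favourable alternative, 160, it is 40 / 160 / 24 × 1000 = 10.4 mcg/hr for entry and twice that, 20.8 mcg/hr, for the upper band. At that end the entry shortfall is therefore slight (38.4 against 40), while the band discrepancy is still 80 / 38.4 = 2.1-fold.

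**5. Secondary check on the 28.5 mg figure.** With the sublingual row and the stated bioavailability, 4 mg weekly is 0.571 × 120 = 68.6 to 0.571 × 160 = 91.4 mg/day MED, not 28.5. If 50 is instead read against parenteral morphine and converted with the 30:10 ratio, it is 0.571 × 150 = 85.7 mg/day, so that reading does not recover 28.5 as an oral MED either.

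**The case against.** The best defence is route of administration. Table 3 is laid out by route, and morphine itself differs three-fold in it. Ratios of 20 (sublingual), 100 (buccal) and 333 (patch) are ratios of nominal doses and need not agree with one another or with a subcutaneous factor. A sublingual factor well below a subcutaneous one is what the 6- to 8-fold bioavailability would lead one to expect. This stands: the spread from 20 to 333 is not in itself an error, and the nominal sublingual and buccal ratios need not equal 50. It does not rescue the patch row, because the route-adjusted conversions in the table above still stop at about 38 mg/day.

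Second, MED is not the only safeguard. Buprenorphine users must meet the Day 1 COWS and average-pain criteria and receive the Buprenex test dose. CAM2038 follows only if they tolerate it and pass the QTcF and COWS checks. The investigator also has discretion under exclusion criterion 2. This is correct, but none of these steps sets or revises the MED or the band.

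Third, calling 50 the more conservative choice is accurate within the 25-50 range of Section 4.2, since the higher factor gives the higher MED for a given CAM2038 dose. That also stands, and it leaves the conflict with Table 3 untouched.

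**Conclusion.** The conflict is real and lies within one section. Table 3's patch row implies 333 where the dose rationale uses 50, a 6.7-fold difference, and nothing in the documents explains it. A 10 mcg/hr patch user is at 80 mg/day by Table 3, 12 mg/day by the dose rationale, and about 18-38 mg/day by the other conversions. Table 3 admits that subject to the upper band; none of the others reaches even the entry criterion. The assignment to the upper band is the firmer part of this; the entry part is close at the top of the range. Secondarily, the sublingual row with the stated bioavailability implies 69-91 mg/day for 4 mg weekly, against 28.5 stated.

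This rests on the labelled patch rate being the delivered rate. Buccal bioavailability, the route behind the 25-50 range, and the number of subjects on buprenorphine at screening are not given, so the effect on the trial population cannot be sized.

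A reader might infer more than the documents support:

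- **That 50 underpins the 40 mg/day entry threshold.** The sentence names subjects on at least 30 mg of morphine. The link to 40 and 80 is only indirect, through Table 1's 75% column (30 and 60 mg, against 28.6 and 57.1 mg for 4 and 8 mg weekly).
- **That the starting-dose statement is wrong for all subjects**, for example because 4 mg weekly at 333 is 190 mg/day. That applies a transdermal ratio to a subcutaneous depot, which no passage does; the 69-91 mg range is likewise a derived product and not a protocol figure.
- **That lower patch strengths also qualify.** Table 3 has only the 10 mcg/hr row, so this would be extrapolation.

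**What to change.** Reconcile Table 3's buprenorphine rows, above all the patch row, with the factor of 50 in Section 4.3 and the bioavailability statement in Section 4.1.1. Restate whichever figure the sponsor finds wrong, and say for each factor which buprenorphine route and which morphine route it refers to. Screening MED, the 40-79 / at-least-80 band and the MED quoted for the starting dose should then rest on one consistent conversion. No view is taken on which factor, dose or rule is right.

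The cost is a corrected table and one paragraph in a protocol amendment. A few subjects on buprenorphine at screening may change band or eligibility.

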4.3.1. Rationale for repeat-site injections

A 9-month study in beagle dogs has been conducted to characterize the chronic systemic toxicity of CAM2038 q1w and CAM2038 q4w SC administration in beagle dogs. Assessments included evaluation of local injection site tolerability and toxicokinetic evaluation at steady-state. Corresponding vehicle placebos and saline were used as controls. A total of 8 injection sites on the back were used. Injection sites were rotated as follows:

- For the q1w: CAM2038 q1w (32 mg/injection), vehicle placebo and saline injections were administered once every week. The injection sites were rotated so that each site was re-used once every eighth week over the course of the study.
- For the q4w: CAM2038 q4w (128, 160 or 192 mg/injection), vehicle placebo and saline. Injections were administered once every 4 weeks. The injection sites were rotated so that each site was used once, except for the last three-monthly injections which were all administered at one site.

The beagle dogs tolerated 39 weekly SC doses of CAM2038 q1w drug product at 32 mg/dose or the CAM2038 q1w placebo control, or 10 doses given once every 4-weeks of CAM2038 q4w drug products at 128, 160, or 192 mg/dose or the CAM2038 q4w placebo control. The CAM2038 drug products and placebo controls had no discernible effect on dermal irritation (erythema, or eschar), overall food consumption, ophthalmologic parameters, clinical pathology endpoints (hematology, coagulation, clinical chemistry, and urinalysis), or organ weights.

Injection site reactions were limited to the presence of Grade 1 edema/swelling, which was considered to represent the injection depot matrix (IDM). Most animals given the BPN-containing CAM2038 drug product formulations or the corresponding placebo controls had Grade 1 (“very slight”) IDM at the sites of injection following dosing. There were no observed differences noted between the sites dosed with BPN-containing CAM2038 drug products and placebo controls.

Additionally, there was no apparent increase in the severity of IDM swelling with repeated injections at the same injection site. Discernable swelling associated with the IDM generally resolved between 60 and 144 days after dosing administration.

This study demonstrated that repeat injections could be safely performed at the same site every 4 weeks with the highest volumes and doses of CAM2038, without any associated deleterious effects.

5. STUDY OBJECTIVES

5.1. Primary Objective

The primary objective of this study is to evaluate the efficacy of long-acting SC injectable depots of BPN (CAM2038 once-weekly [q1w] and CAM2038 once-monthly [q4w]) compared to placebo on average pain intensity (API) scores, as measured on an 11-point, numerical rating scale (NRS-11) in subjects currently taking daily opioids for moderate to severe CLBP.

5.2. Secondary Objectives

The secondary objectives of the study are:

- Change from baseline in the weekly average of daily worst pain intensity (WAWPI) scores at Week 12 of the Double-Blind Phase based on the NRS-11.
- To evaluate the safety and tolerability of treatment with CAM2038 q1w and CAM2038 q4w in subjects currently taking opioids for moderate to severe CLBP.

5.3. Open Label Safety Extension Objectives

5.3.1. Primary Objectives of Open Label Safety Extension

The primary objective of the open label extension phase is:

- To evaluate the safety and tolerability of treatment with CAM2038 q1w and CAM2038 q4w up to 52 weeks in subjects with moderate to severe chronic pain requiring daily treatment with opioids.

5.3.2. Secondary Objectives of Open Label Safety Extension

The secondary objectives of the open label extension phase are:

- Evaluate the steady-state PK of BPN for CAM2038 q1w and CAM2038 q4w in subjects with moderate to severe chronic pain requiring daily treatment with opioids
- Evaluate the efficacy and safety of CAM2038 q1w and CAM2038 q4w administration for up to 52 weeks in the treatment of subjects with moderate to severe chronic pain requiring daily treatment with opioids.

6. INVESTIGATIONAL PLAN

6.1. Overall Study Design and Plan

This is a Phase III, placebo-controlled, multicenter study with an enriched-enrollment withdrawal (EEW) design to evaluate the efficacy and safety of CAM2038 in opioid-experienced subjects with moderate to severe CLBP that requires continuous, around-the-clock (ATC) opioid treatment ≥ 40 mg MED. An overview of the study design is provided in [Figure 1](#). The study includes 5 phases: A Screening Phase (up to 2 weeks), a Transition Phase (up to 2 weeks), an Open Label Titration Phase (up to 10 weeks), a Double-Blind Treatment Phase including a Final Study Visit (12 weeks), and a Follow-up Phase (4 weeks) The overall duration of participation of the core phase is up to 30 weeks, from the Screening Phase through the Follow-up Phase. Subjects who complete the Double-Blind Treatment Phase will be offered the opportunity to continue treatment in an Open Label Safety Extension Phase for up to 60 weeks. In addition, so called “de novo” subjects may be enrolled in the Open Label Safety Extension Phase. These subjects may proceed directly from the Open Label Titration Phase to the Open Label Safety Extension Phase without participating in the Double-Blind Treatment Phase.

Subjects will record their API at Screening and prior to the test dose on a paper diary at the site. Throughout the study, after subjects receive their first CAM2038 injection, they will record their WPI and API using the NRS-11 in an electronic diary. Subjects will be instructed to record their WPI and API once daily between 18:00 and 23:59 (i.e., 6:00 pm and 11:59 pm). Subjects will be instructed to make all attempts to record their pain scores at the same time of day throughout the study. In addition, subjects will be instructed to record their pain intensity in the electronic diary on the NRS-11 “at that moment” prior to taking rescue medication. Rescue medication use will also be recorded in the electronic diary.

[Table 5](#), [Table 6](#), and [Table 7](#) provide additional information on the baseline, efficacy, and safety assessments included in the study. Efficacy endpoints and statistical analyses are described further in [Section 9.6](#) and [Section 11.3](#), respectively.

6.1.1. Transition Phase

Following Screening and confirmation of eligibility, subjects will enter a Transition Phase of up to 2 weeks during which their current opioid dose will be down-titrated by approximately 25% per day to:

- ≤ 80 mg/day MED (for subjects whose opioid dose at screening is > 80 mg MED)
- or to ≤ 40 mg/day MED (for subjects whose opioid dose at screening is between 40-79 mg/day MED).

Following the down titration, subjects will be transitioned to an immediate-release (IR) morphine for at least 2 days before they enter the Open-Label Titration Phase, as follows:

- 15 mg 4 times daily [QID] for subjects whose screening MED was ≥ 80 mg/day
- 15 mg 3 times daily [TID] for subjects whose screening MED was 40-79 mg/day.

Subjects who were previously on BPN prior to Screening will not need to participate in the morphine IR phase. However, subjects who were previously on BPN will be required to refrain from taking BPN for

12-24 hours as a washout prior to starting open label titration on CAM2038.

6.1.2. Open Label Titration Phase

Following the morphine IR treatment, subjects will enter the Titration Phase. On Day 1 of the Titration Phase, subjects will return to the clinic after a washout of at least a 12-hour from their last morphine IR dose, or 12-24 hours from their last BPN dose. Subjects who report a CLBP of ≥ 5 on the API scale and have a Clinical Opiate Withdrawal Scale (COWS) score of ≥ 5 , will receive a BPN test dose (Buprenex 0.30 mg IM injection) at the clinical site. After the Buprenex test dose, subjects will be assessed for any changes in QTcF (Fridericia's corrected QTc) and withdrawal. Subjects who tolerate the BPN test dose, do not show an increase >30 ms in QTcF within 1 hour after the test dose, and have a COWS score of <5 within 15 minutes after the test dose will receive the first dose of SC CAM2038 q1w within 4 hours (+30 minutes) after the test dose (4 mg CAM2038 for subjects whose screening MED was between 40 mg/day and 79 mg/day; and 8 mg CAM2038 for subjects whose screening MED was ≥ 80 mg/day).

During the first week of the Titration Phase, subjects who experience significant pain may, at the discretion of the investigator, receive an additional 4 mg (for subjects whose screening MED was 40-79 mg/day) or 8 mg CAM2038 (for subjects whose screening MED was ≥ 80 mg/day), on Day 3, 4 or 5. Dose adjustments will be made by increasing or decreasing the dose level of CAM2038 q1w at the scheduled weekly visits (doses of 4 mg, 8 mg, 12 mg, 16 mg, 24 mg, or 32 mg per week). Subjects who require doses >32 mg/week will be discontinued from the study.

Rescue medication, consisting of hydrocodone/acetaminophen 5 mg/325 mg every 4 to 6 hours (q4-6h), may be taken as needed (prn) up to 15 mg/975 mg/day (three tablets) for subjects whose screening opioid dose was between 40 and 79 mg/day MED or 30 mg/1950 mg/day (six tablets) for subjects whose screening opioid dose was ≥ 80 mg/day MED. The goal of the Titration Phase is to achieve a stable dose of CAM2038 q1w that produces analgesia, by the end of the 10-week period.

Eligible subjects will receive CAM2038 titrated to a dose that meets the following criteria (see also Section 7.4):

- Provides analgesia (i.e., 7-day mean API ≤ 4)
- The API is at least 2 points below the value at the start of CAM2038 titration
- The dose of CAM2038 is well-tolerated for 7 days before randomization (no adverse effects that require a change in study dosing or interruption)
- Subject does not require, on average, more than one dose of rescue medication per day over the 7 days before randomization

[figure not shown]
